8.5. Sample size

To estimate the sample size for a given power, we note that the variance of the change in mean for one of the two groups is given by $V=SD^2/n$ where SD is the standard deviation of the changes across people within a group and n is the number of subjects in each group. Then, the main hypothesis that the two treatment groups change an equal amount is just a two sample comparison for which the sample size is given $V*\{Z(1-\beta) + Z(1-\alpha/2)\}^2 / \delta^2$ where $Z(1-\beta)$, $(1-\alpha/2)$, are the $1-\beta$ and $1-\alpha/2$ quantiles for the standard normal distribution, and δ is the anticipated difference in change from baseline between the two groups³⁹. Figure 3 shows the requisite sample size per group to attain 80% and 90% power respectively for varying values of the difference in change denoted δ on the horizontal axis. For the estimated minimally important difference (MID) of pct950, (delta = 2%/year), SD = 4%/year, alpha = 0.05 two-sided, and power = 90%, the required sample size is 88 participants per group which is inflated 20% (110 per group) to account for poor adherence, missing data, or to have adequate power to detect smaller treatment effects.

[figure not shown]

Figure 3: Sample size required for indicated power and difference (Delta) between change for losartan and placebo groups, assuming alpha=0.05, and standard deviation of the change within a group of 4.0

9. Protection of human subjects

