7.3. Randomization

Treatment assignment will be randomly allocated in a 1:1 ratio with stratification by clinic using a permuted block randomization scheme. Randomization will occur at V2 after the participant meets all eligibility criteria. The clinic staff will complete a randomization form for each eligible participant and enter it into a web-based randomization system. Eligibility criteria are verified via computer program, which then provides a unique study treatment assignment number according to an encrypted table on the server; the assignment number will correspond to a specific drug bottle.

The initial drug supply will be dispensed and a tear-off label will be affixed to a study form to provide an audit trail for drug distribution.

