
The primary analysis will be intention-to-treat so that the indicator trt is the group to which the person is randomized without regard to whether they complied with the treatment assignment or not. We anticipate some degree of loss-to-follow-up (less than 10%) that will not affect our analyses. However, the regression model above will be estimated using the method of maximum likelihood so that missing data will effectively be imputed by their expected values given the other measurements. If the loss-to-follow is 10% or greater, then multiple imputation will be used to construct the 95% confidence limits for β_1 estimated across 50 imputations of the dataset.

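### Do the misprinted sample-size formula and the single shared inflation allowance leave the trial short of 90% power?

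*Combined protocol and SAP*

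**What the plan says.** Section 8.5 describes the main hypothesis test as "just a two sample comparison for which the sample size is given" by a formula. That formula multiplies V by the squared sum of the two normal quantiles and divides by delta squared. V has just been defined as SD²/n, the variance of the mean change in one group. The inputs are a difference of 2% per year in pct950, "alpha = 0.05 two-sided, and power = 90"%, and, in the Figure 3 caption, a "standard deviation of the change within a group of 4.0".

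The result is then stated: "the required sample size is 88 participants per group which is inflated 20% (110 per group) to account for poor adherence, missing data". The sentence goes on, after the word *or*, to name a third use: adequate power for smaller treatment effects. No percentage is assigned to any of the three, and no adherence rate is given anywhere.

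Two other statements matter. Section 8.1 expects loss to follow-up of less than 10%. It also fixes the analysis population: "The primary analysis will be intention-to-treat so that the indicator trt is the group to which the person is randomized", whether or not they complied. Section 7.3 gives equal allocation.

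**The concern.** Three things look wrong on a first reading.

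- **The formula.** As printed it has n on both sides and no factor 2. Replacing V by SD² to make it usable gives 43 per group, about half of 88, so a reader could suspect that the trial was sized with the wrong expression.
- **The inflation.** An increase of 20% on 88 is 106, not 110.
- **Adherence.** Dividing by 0.80 corrects for participants without an outcome. Participants who stop the drug but return for the 48-week scan stay in the intention-to-treat comparison and shrink the difference, and the required n then grows with the square of that shrinkage. If the whole reserve went on missing scans, almost nothing would be left for adherence.

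If this meant that 90% power was not really provided, a null result might be read as stronger evidence against the 2-point minimally important difference than the design supports.

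**Working it through.** **Inputs.** Delta = 2, SD = 4, two-sided alpha 0.05, power 90%, and 88 then 110 per group (section 8.5); 1:1 allocation (section 7.3); loss under 10% and intention-to-treat (section 8.1). The dilution rates below are assumptions, because the documents give none.

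**1. The plan's figure of 88.** The standard formula is n per group = 2 × SD² × (z₀.₉₀ + z₀.₉₇₅)² / delta².

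- (1.2816 + 1.9600)² = 10.51
- n = 2 × 16 × 10.51 / 4 = 84.06, so 85 per group
- The exact two-sample t calculation gives 86.
- Power at 88 by noncentral t is 91.0%.

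So 88 is two or three above the requirement. Without the factor 2, 16 × 10.51 / 4 = 42.03, so 43 per group, with 63% power. The plan did not use that figure: 88 is a two-sample result, and the error lies only in how the formula was written down.

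**2. The step from 88 to 110.** 88 / (1 − 0.20) = 110 exactly, whereas 88 × 1.20 = 105.6, or 106. The number is the usual correction for losing 20% of participants; the wording is loose.

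**3. What 110 per group delivers.** Let m be the proportion of scans missing and p the proportional dilution of the effect. The evaluable n is 110 × (1 − m) and the effect is 2 × (1 − p). Power by noncentral t:

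| Missing scans | Evaluable per group | p = 0 | p = 5% | p = 10% | p = 20% |
|---|---|---|---|---|---|
| 0% | 110 | 95.8% | 93.9% | 91% | 84% |
| 10% | 99 | 93.8% | 91.4% | 88.3% | 80% |
| 20% | 88 | 91.0% | 88.0% | 84.3% | 75% |

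The effect detectable with 90% power is 1.756 at 110 per group, 1.852 at 99 and 1.966 at 88. The largest dilution that keeps 90% power is therefore:

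- no missing scans: 1 − 1.756/2 = 12%
- 10% missing: 1 − 1.852/2 = 7%
- 20% missing: 1 − 1.966/2 = 2%

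**4. Can a null result be misread?** Section 8.1 bases inference on a 95% confidence interval. With 99 per group its half-width, before any gain from covariates, is about 1.96 × 4 × √(2/99) = 1.11. Under the planned SD, an estimate near zero gives an interval that excludes 2. That conclusion about the intention-to-treat effect comes from the interval, not from the planned power.

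**The case for a change.** The best argument for acting is that section 8.5 names poor adherence as something the inflation covers, yet the arithmetic is a missing-data correction only. Even if the 20% is taken as a combined total, 10% missing with 10% dilution gives 88.3%, and a full 20% spent on non-adherence gives 84%. The protocol also keeps participants who stop treatment in follow-up (sections 7.5 and 7.6), so dilution is a real mechanism here. Section 6.2 quotes losartan discontinuation for adverse or side effects of 2.3% in controlled trials and 19% in a diabetic nephropathy trial. At 19%, if those who stop get no benefit, power would be about 85% with no missing scans and 81% with 10% missing.

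Much of this stands as description. The plan gives no split and no adherence rate, so the cover for adherence cannot be checked exactly, and it is smaller than the cover for missing scans.

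It does not show that the planned power fails. The reserve is one allowance whose uses are joined by *or*; it does not promise 20% for each. The 19% comes from a different population, as does the 2.3%, at which power stays above 90% with 10% missing. Zero benefit in everyone who stops is the worst case. A participant who stops the drug and also misses the final scan reduces n without also diluting the observed difference, so adding the two losses in full overstates the damage.

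**Conclusion.** No change follows. The formula is a clerical slip: from the stated inputs the correct expression gives 85 (86 by t-test), and the plan's 88 errs on the safe side. The 20% describes a division by 0.80, and 110 is right on that reading.

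The unstated split of the reserve is a missing detail that a reader can fill from section 8.1. At the expected ceiling of 10% loss, power is 93.8% at the full effect and stays at 90% or more up to about 7% dilution. The shortfall at 10% missing with 10% dilution is under 2 points. The figures of 84%, 80% and 75% all need 20% dilution, which the documents do not plan for.

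Rewriting the section would alter neither the enrolment of 220, nor the model, nor the decision rule, nor how a null result is read. This conclusion rests on the plan's delta of 2 and SD of 4, and on loss staying below the 10% it expects. If adherence proved poor, the cost would be some power against the full 2-point effect, without bias in the intention-to-treat comparison.

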9.1. Recruitment and consent procedures

Participants will be recruited by each participating clinic by their own methods. These methods may include social media campaigns, solicitation in physician offices, clinics, workplaces, and public media advertisements, patient and research subject registries and electronic medical records. All public advertisements are subject to approval by the local Institutional Review Board (IRB) and must indicate that it is a research study. The NEMO will help coordinate recruitment among clinics and promote sharing of effective recruitment strategies within the network. The study encourages prescreening of participants for prior HRCT evidence of emphysema, presence of comorbidities, and concurrent medications.

Potential enrollees will be approached either in person, by telephone or by mail to establish general eligibility criteria. A general description will be provided prior to their initial visit. If the potential enrollees are interested in participating, they will meet with the study coordinator and local physician co-investigators to review the study and to ask questions. They will be asked to sign consent, and if appropriate provide assent, and undergo the screening procedures.

The consent form will be subject to approval by the clinical center IRB. A copy of the consent form will be given to each participant, and the signed original will be kept in the participant's research chart.

9.2. Potential risks and procedures to minimize risk to the participants

During this study, participants will continue to receive their usual care for COPD as per their treating physician. If any medical illness requiring treatment is discovered during the collection of data for the course of this study protocol, individuals will be referred to their primary care providers for further evaluation and treatment.

Potential risks associated with this study are outlined below. In order to minimize risk to participants, the following actions will be taken.

- Treatment with losartan: Losartan is an FDA-approved angiotensin receptor blocker that is widely prescribed for treatment of hypertension, heart failure, and for renal protective effects in diabetics. The dose proposed in this study is well-tolerated by non-hypertensive patients without significant effect on blood pressure. The most common side-effects are fatigue and dizziness. Serious adverse events that are rare include angioedema, hypotension, renal dysfunction or failure, blood dyscrasias, hepatitis, or rhabdomyolysis. In order to minimize risk to participants, the following actions will be taken. The first dose of medication will be administered in the clinic (50mg/placebo) and the participant observed for two hours thereafter with a blood pressure check for

hypotension. Participants with hyperkalemia, significant renal dysfunction, or who are taking potassium supplements will not be enrolled into the study. Participants are given written descriptions of potential side-effects and appropriate means of dealing with them. For example, mild postural hypotension can often be minimized by arising slowly and maintaining adequate hydration. Skin rashes, palpitations or other moderate or severe (defined as those that interfere with usual daily activities) adverse events without other clear explanation should warrant immediate cessation of treatment and notification of study personnel. If the study physician warrants that it is unlikely that the event is related to the medication, then it may be restarted after resolution or stabilization of the adverse event.

After the initial two weeks of treatment, subjects will return for titration up to 100mg of losartan or two placebo capsules. They will be observed for one hour thereafter with a blood pressure check for hypotension. Adverse events will be monitored at each of the study visits by specific and open-ended questions. Losartan is a potential human teratogen particularly in the second trimester of pregnancy. Therefore, pregnancy testing will be performed prior to randomization and at each visit for persons of child bearing potential. As well, participants of child-bearing age will be counseled on the risk of pregnancy as delineated in the consent form.

- High Resolution Computed: Tomography: HRCT is a standard medical procedure for imaging of the lung, is widely used in research and clinical care of patients with COPD, and is recommended by the US Preventive Services Task Force for annual lung cancer screening. Risks to the volunteers are minimal. This will involve a small amount of radiation exposure to our subjects. The HRCT Dose is standardized so each manufacturer and model are matched within $\pm 3\%$ of the Target CTDIvol. For the current proposal, to limit the risk of radiation exposure, we have determined what we consider the best balance between high quality data and minimal radiation exposure. We intend to perform two high-resolution chest HRCT scans of the subjects over 48 weeks. The chest HRCT protocol will be adjusted; based on the weight of the subjects. For average-weight adults of 80 kg, the effective dose estimation for each CT scan, is 4 mSv. The total effective dose for the study protocol will be 8 mSv. This compares to the annual allowed limit on radiation workers is 50 mSv in the US. The risk of radiation overexposure will be mitigated by ensuring that all centers are certified for performance of the tests in an ACR accredited facility that performs the required daily calibration of instrumentation. Moreover, prior to participant enrollment and regularly during the trial, HRCT scanners at each site will be calibrated using a Lung Phantom (e.g. CPT674, The Phantom Lab, Salem, NY) and reviewed by the HRCT reading center. While there are some variations between HRCT scanners, a standardization of the parameters and exposure levels has been developed to allow multiple scanners to output reliable quantitative measures and minimize risk across a given patient population.

There is risk of discomfort while lying in the scanner, or cough with breath holding, and participants will be continuously supervised by radiology staff during the procedure.

Although the scans are done only for research purposes, we are requiring that all HRCT scans be interpreted by a certified radiologist on site. The scans will be inspected for adequate inspiration, absence of motion artifact and inclusion of all parts of the chest. It may occur that other findings are found on these images that may represent clinically significant findings (e.g. lung nodules). If any incidental findings are discovered during study, the clinical site study physician will be notified, the information will be given to the participant and, with their permission, the information will also be transmitted to the participant's usual care-giver for appropriate medical care or follow-up.

- Pulmonary Function Testing: Spirometry is a routine clinical procedure that entails little risk. Participants are coached to make repeated forceful breathing efforts that sometimes makes their chest sore for a day or so. In some unusual cases participants may become light-headed during these efforts. The risk to the participant is minimized by having these procedures done with the participant seated during the testing.
- Phlebotomy: This may cause pain during the insertion of the needle or slight bruising afterward. This risk is minimized by the use of disposable single use needles, trained personnel, and application of pressure after the blood draw.
- Questionnaires: Health History acquires information that is routinely collected in the process of medical care of patients with COPD. There are no significant physical risks from these procedures. As with all medical information, there is always the risk of psychological distress if personal health information is not held confidential within the wishes of the participant. In order to minimize this risk, electronic medical records are held in HIPAA compliant password-protected databases, and written information is stored in locked files or file-rooms when not attended by study personnel. Medical information is provided to treating sources consistent with HIPAA guidelines.
- Physical examination: Physical examinations and the collection of vital sign including pulse oximetry are usual medical procedures for patients with COPD. There are no significant physical risks from these procedures.

9.3. Data and safety monitoring plan

A Data and Safety Monitoring Board (DSMB) will be appointed by NHLBI to monitor the entire PTC and will be chartered and managed by the NEMO. The DSMB will serve in a consultative capacity to NHLBI and will make recommendations regarding the initiation and conduct of the study to the institute. The primary responsibility of the DSMB is to protect participants but may also have recommendations regarding the scientific conduct of the study to optimize the information gained from the study. Typically, the DSMB would meet every six months or more frequently to review the progress of the trial. The investigators will present the DSMB with study performance data including screening and enrollment data, and measures of data quality and

timeliness. Safety data will include reporting of adverse events, protocol deviations, and unexpected or unusual events that may affect the safety or scientific validity of the study; these will be reported by treatment group. After sufficient data are acquired, the DSMB may request to see outcome data, although for this type of translational study, it is unlikely that any finding would be sufficiently clinically directive to use for interim recommendations. Accordingly, we are not proposing formal interim efficacy analyses or stopping guidelines.

Reporting of Serious Adverse Events

A serious adverse event (SAE) is an adverse event that results in one of the following outcomes: death, a life-threatening adverse drug experience, inpatient hospitalization or prolongation of existing hospitalization, a persistent or significant disability/incapacity, or congenital anomaly/birth defect. Also, important medical events that may not result in death, be life-threatening, or require hospitalization may be considered a serious adverse event when, based upon appropriate medical judgment, they may jeopardize the patient or subject and may require medical or surgical intervention (treatment) to prevent any of the outcomes previously listed in this definition. When an investigator or clinical center staff member becomes aware of an SAE, it should be reported to the DCC within 72 hours with follow up reporting until the event is terminated. The DCC will send these reports to the DSMB, the network coordinating center, and NHLBI representatives; these reports will be distributed with a ballot for DSMC members to indicate whether an ad hoc meeting should be convened to discuss the SAE, The DCC will distribute reports of SAEs that are possibly related to the study treatment or study participation all centers for review by their local IRBs and to the DSMB in a timely fashion.

Interim Analysis for Safety

The DSMB will evaluate reported adverse events and treatment-emergent symptoms by treatment group at each meeting. These analyses will review both expected and unexpected events by severity and treatment-emergent symptoms reported by participants at follow-up visits. A standard set of symptoms will be queried at each visits along with an open-ended question about other symptoms. Analysis of treatment effects on adverse events and treatment-emergent symptoms will include cumulative percentages of participants with events by severity. While no formal stopping guidelines for safety are planned, the DSMB will evaluate whether the burden of treatment exceeds the potential benefits of treatment at each meeting and be responsible for making a recommendation to the NHLBI regarding continuation of the trial.

9.4. Data confidentiality

Participant data, which includes identifiable personal health information (PHI), are collected at each of the clinical sites. PHI will be stored at each of the clinical sites in accordance with HIPAA regulations and local university and hospital policies. This includes the storage of PHI in locked cabinets or rooms, limited access to secure data areas by certified study personnel, password protection for electronic medical records, and explanation of HIPAA regulations on the study consent form. Analytic files will not contain personal identifiers (e.g. name, address). All

reports/manuscripts will be prepared in such a way that individual participants cannot be identifiable.

Data such as lung function or laboratory tests that are collected as part of this study may be transmitted to the participants treating physicians with the consent of the participant. Participants will be informed in the consent that PHI may also be disclosed for auditing purposes by the NIH or other regulatory bodies and is subject to subpoena.

All HRCT scans will be de-identified at the scanning institution and a unique study ID will be assigned by the DCC. De-identified HRCT scans are transmitted electronically to the NEMO, then to the DCC and are logged, quality-controlled, and analyzed in a blinded fashion by a trained technician using a semi-automated Slicer workstation at the HRCT reading center supervised by [name]. HRCT scans and other data will also be transmitted to the NEMO at University of Pittsburgh for the purposes of ensuring quality control.

Personal identifiers (e.g. name, address, EMR number) are not transmitted to the DCC or central laboratory in that all biospecimens and records are identified by a study ID, and other identifying information such as names are not entered into the central study database. Source records that are transmitted to the DCC for data quality audits have identifying information redacted. No highly confidential information is routinely collected, although the data collection does include PHI, so a breach of confidentiality would constitute a HIPAA violation. If a participant is harmed from this study as a consequence of negligence, then the investigators or University might be liable for damages.

We will advise participants that the U.S. Department of Health and Human Services has the right to inspect medical records relating to this research for the purposes of verifying data. Where data are shared with other research entities, it will comply with the HIPAA definition of a limited dataset, and appropriate IRB approvals and waivers will be obtained.

10. Acronyms

ACE	Angiotensin converting enzyme
ACR	American College of Radiology
ARB	Angiotensin receptor blocker
AT1	Angiotensin 1
ATS	American Thoracic Society
ATS-DLD	modified American Thoracic Society - Division of Lung Disease questionnaire
BD	Bronchodilator
BMI	Body Mass Index
BP	Blood pressure
CAT	COPD Assessment Test
CBC	Complete blood count
CMP	Comprehensive metabolic panel
COPD	Chronic Obstructive Pulmonary Disease
DCC	Data Coordinating Center
DSMB	Data and Safety Monitoring Board
ERS	European Respiratory Society
FDA	US Food and Drug Administration
FEV ₁	Forced Expiratory Volume in one second
FVC	Forced Vital Capacity
GFR	Glomerular Filtration Rate
HIPAA	Health Insurance Portability and Accountability Act
HIV	Human immunodeficiency virus
HRCT	High resolution computed tomography
HU	Hounsfield Units
IRB	Institutional Review Board
LEEP	Losartan Effects on Emphysema Progression
LFT	Liver Function Test
MDI	Metered dose inhaler
mEq/L	Milliequivalent/ liter
MID	Minimal important difference
mMRC	Modified Medical Research Council
mSv	millisievert
NHANES	National Health and Nutrition Examination Survey
NHLBI	National Heart, Lung, and Blood Institute
NSAID	Non-steroidal anti-inflammatory drug
OC	Operations Committee
PFT	Pulmonary Function Test
PHI	Protected health information
PROMIS-20a	Patient Reported Outcomes Measurement Information System: Physical Function – Short Form 20a
RENAAL	Reduction of Endpoints in NIDDM with the Angiotensin II Antagonist Losartan study
SAE	Serious adverse event
SD	Standard deviation
SpO ₂	Peripheral capillary oxygen saturation
TGFb	Transforming Growth Factor Beta
SGRQ-C	St. George's Respiratory Questionnaire for COPD Patients
TLC	Total Lung Capacity

11. Literature cited

- 1 US Burden of Disease Collaborators. The state of US health, 1990-2010: burden of diseases, injuries, and risk factors. *JAMA*. 2013 Aug 14;310(6):591-608.
